PCI patients requiring OAC [17]. Most recently a scoring system called ABCD-GENE has been developed which allows to readily identify patients with HPR status with high accuracy [18]. In particular, this scoring system integrates clinical (age, body mass index, chronic kidney disease, and diabetes mellitus) and genetic (CYP2C19 alleles) variables. Patients with a high ABCD-GENE score (≥10) have an increased risk of HPR and adverse ischemic events [18]. However, data on the impact on platelet inhibitory effects associated with tailored selection of P2Y₁₂ inhibiting agents in this setting remains unexplored.

5. Specific Aims: The aim of the Switching Anti-Platelet and Anti-Coagulant Therapy (SWAP-AC) – 2 Study is to assess the pharmacodynamic effects of different P2Y₁₂ inhibiting therapy (clopdiogrel vs ticagrelor) according to the ABCD-GENE score in PCI treated patients also requiring OAC.

6. Research Plan:

Study design

This will be a prospective study conducted in any patients with CAD, including those with Acute Coronary Syndrome (ACS) undergoing PCI who have an indication to be treated with an OAC. Patients undergoing PCI treated with DAPT during the peri-PCI period and also require OAC as part of their standard of care will be identified. The study will be performed at the Division of Cardiology of University of Florida Health, Jacksonville, Florida (site PI: [name], PhD) and at St. Antonius Hospital in Nieuwegein, The Netherlands (site PI: [name], MD, PhD).

Patients will be recruited within the Cardiovascular services of each Institution. Patients will be screened by Cardiology Research staff, who will verify that all candidates meet inclusion and exclusion criteria. After providing written informed consent, patients will be stratified according to their ABCD-GENE score (using a cut-off of 10) into two cohorts: ABCD-GENE≥10 and ABCD-GENE< 10. The ABCD-GENE scoring system is described in Figure 1.

Figure 1. ABCD-GENE score

ABCD-GENE SCORE		Points
Clinical factors		
THE	Age >75 years	+4
	BMI >30 kg/m²	+4
6	CKD (GFR <60 mL/min)	+3
(3)	Diabetes mellitus	+3
Genetic factors		
	One CYP2C19 LOF allele	+6
-(3)	Two CYP2C19 LOF alleles	+24

Patients will be screened during hospital stay after undergoing successful PCI.

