Results from blood tests performed within the last 30 days will be considered valid for screening. Patients will undergo genetic testing to identify CYP2C19 genetic status using the Spartan assay or central lab. Randomization will occur once genetic testing results become available, ideally prior to hospital discharge. However, for patients discharged

[figure not shown]
before having results available or over the weekend they will be allowed to return for their randomization within 3 days from test results. Patients with an ABCD-GENE≥10 score will be randomized in a 1:1 fashion to ticagrelor (60 mg/bid) or clopidogrel (75 mg/qd). Patients with an ABCD-GENE<10 will be treated with clopidogrel (75 mg/qd).

Since the choice of P2Y₁₂ inhibitor during the PCI procedure may vary (commercially available agents include clopidogrel, ticagrelor and prasugrel), the following recommendations will be made based on the agent chosen and the treatment assignment: a) patients assigned to clopidogrel and also treated with clopidogrel during PCI will continue with a 75 mg/qd maintenance dose for the duration of the study; b) patients assigned to clopidogrel but treated with ticagrelor or prasugrel during PCI will receive a 600 mg loading dose clopidogrel followed by a 75 mg/qd maintenance dose for the duration of the study; c) patients assigned to ticagrelor and also treated with ticagrelor during PCI will continue with ticagrelor 60 mg bid maintenance dose for the duration of the study; d) patients assigned to ticagrelor but treated with clopidogrel or prasugrel during PCI will be administered a 180 mg loading dose followed by a 60 mg bid for the duration of the study. Administration of randomized treatment will occur prior to hospital discharge as would occur per standard of care for administration of the next dose of P2Y₁₂ inhibiting therapy. The use of a loading dose when switching agent is in line with consensus recommendations for switching P2Y₁₂ inhibiting therapy [19]. The clopidogrel 600mg loading dose and 75 mg/qd maintenance dose regimen is in line with practice recommendations [1]. The ticagrelor 180 mg loading dose regimen is in line with practice guidelines; the 60 mg bid maintenance dose regimen was chosen in light of recent data that this dose provides platelet inhibitory effects not dissimilar from the 90 mg bid dosing

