regimen but with less side effects and more efficacious platelet inhibitory effects than clopidogrel, including after PCI [1,20]. All patients will maintain aspirin 81 mg/qd at least for the duration of hospital stay. Aspirin therapy will be discontinued at time of hospital discharge or at 7 days after PCI at the discretion of the treating physician in patients deemed to be at high ischemic risk, as per standard of care for patients requiring concomitant treatment with a P2Y₁₂ inhibitor and an OAC [14,15].

Assigned treatment will be maintained for 30±5 days. PD assessments will be conducted at 3 time points: i) baseline (while on standard of care DAPT therapy): day after PCI, ideally before the administration of the morning dose of P2Y₁₂ inhibiting therapy and OAC (trough levels of platelet reactivity); however, since patients may get discharged the same day of the PCI or may have already taken their daily dosing regimen, blood sampling will be allowed as this does not interfere with the study hypothesis; patients will continue to take their morning dose of aspirin and all other standard of care therapies; ii) 30±5 days after randomization: before (trough levels of platelet reactivity) and 2 hours after (trough levels of platelet reactivity) the administration of the morning doses of P2Y₁₂ inhibiting therapy and OAC (trough levels of platelet reactivity); patients will take all other standard of care therapies. Figure 2 illustrates the overall study design and a further breakdown of what will occur during the course of the study:

- Patients will first be screened by research personnel to see if they are eligible for the study. Results from blood tests performed within the last 30 days which patients would have performed because of their stent procedure will be considered valid for screening purposes.
- If it is a woman of childbearing potential, a pregnancy test will be done. If the subject is found to be pregnant, their participation in this study will end.
- If they are eligible for the study based on the screening results, they will start the study procedures as outlined below:
 - Genetic test buccal swab. This swab is being done to determine CYP2C19 genetic status.
 - The physician will determine the ABCD-GENE score as described in Figure
 1. This score is calculated by looking at the subject's CYP2C19 genetic

status and clinical information, including age, BMI, renal function, and diabetic status.

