Patients with an ABCD-GENE<10 will be treated with clopidogrel (75 mg/qd). Patients with an ABCD-GENE≥10 score will be randomized in a 1:1 fashion to ticagrelor (60 mg/bid) or clopidogrel (75 mg/qd). Assigned treatment will be maintained for 30 +/- 5 days.

Blood will be collected at two visits by inserting a needle into a vein or from a catheter in a vein. The first visit will be after the PCI ideally before the subject has taken their antithrombotic medications (baseline); however, since patients may get discharged the same day of the PCI or may have already taken their daily dosing regimen, blood sampling will be allowed as this does not interfere with the study hypothesis. The second visit will be 30 +/- 5 days later. At this visit there will be two blood draws: the first before the subject has taken their antithrombotic medication (trough) and second 2 hours after the subject has taken their antithrombotic medication (peak).

PD measures will include a multitude of assays aimed to assess various measures of platelet reactivity, including purinergic and non-purinergic signaling pathways, and thrombin generation, as described below. Although the study will have an open-label design, laboratory personnel will be blinded to treatment assignments. Compliance with antithrombotic therapies will be assessed by interview and pill counting. During study treatment, major adverse cardiac events (death, myocardial infarction, stroke, and urgent revascularization procedures), serious adverse events (bleeding and other adverse events),

as well as non-serious adverse events will be collected. After completing the study, patients will resume an antithrombotic treatment regimen at the discretion of the treating physician.

Study population

A total of 84 CAD patients will be recruited In particular, 42 patients with an ABCD-GENE≥10 will be included and randomized to ticagrelor (n=20) or clopidogrel (n=20), while 42 patients will be in the ABCD-GENE<10 cohort. Patients will need to meet the following study entry criteria:

Inclusion criteria:

- Age \geq 18 years
- Willing and able to provide written informed consent
- Undergone successful PCI and treated with DAPT (aspirin plus a P2Y12 inhibitor) per standard of care
- On treatment with a novel oral anticoagulant (apixaban, dabigatran, edoxaban, or rivaroxaban) for any indication (dosing regimen will be according to standard of care and at the discretion of the treating physician)

Exclusion criteria:

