Additional exploratory end points will include the comparisons between clopidogrel-treated patients with ABCD-Gene score<10 and the other 2 arms, as well as comparisons between groups of rates of HPR. For baseline characteristics, categorical variables will be expressed as frequencies and percentages; continuous variables will be

presented as mean ± SD or median [IQR]. Continuous variables will be analyzed for normal distribution with the Kolmogorov-Smirnov test. Comparisons for the primary end point as well as for other intergroup comparisons of continuous variables will be performed with an analysis of covariance with a general linear model with baseline value of the corresponding platelet function test as a covariate. Intragroup comparisons will be performed using a mixed linear model. Comparisons for categorical variables, including rates of HPR will be performed with the Chi square test or Fisher exact test. A p-value < 0.05 will be considered statistically significant. Statistical analysis will be performed with SPSS version 25 software (SPSS Inc.). Data analysis will be performed at the University of Florida. Data transfer will occur in a HIPAA de-identified manner. Data from The Netherlands will arrive coded so that source of data can be easily known."

The PD population will include all patients with PD data and without a major protocol deviation thought to affect significantly the PD of ticagrelor or clopidogrel. The PD population will be used for analysis of all primary and secondary PD variables. Erroneously treated patients (eg, those randomized to one treatment but actually given the other) will be accounted for based on the actual treatment received.

All patients who received at least 1 dose of study drug will be included in the safety population. Safety will be evaluated by assessment of adverse events (including bleeding and ischemic). Adverse events will be collected up to completion of the study. Bleeding events will be classified according to BARC (Bleeding Academic Research Consortium) criteria [27]. Stent thrombosis will be classified according to ARC (Academic Research Consortium) definitions [28]. MI, including peri-procedural MI, will be defined according to the universal definition [29]. Ischemic stroke will be defined as

an ischemic cerebral infarction caused by an embolic or thrombotic occlusion of a major intracranial artery. Death will be considered cardiac in origin unless obvious non-cardiac causes can be identified.

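### CYP2C19 loss-of-function status is known before allocation but is neither a stated randomisation stratum nor a term in the primary ANCOVA, so a cheap gain in balance and precision is missed

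*Combined protocol and SAP*

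**What the plan says.** Section 6, Study design, puts the genotype before the allocation: "Randomization will occur once genetic testing results become available". Every randomised patient therefore has a CYP2C19 result on file.

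The word stratified appears once in connection with allocation: "patients will be stratified according to their ABCD-GENE score (using a cut-off of 10) into two cohorts". That sorts patients into the randomised and non-randomised cohorts. Within the upper cohort, the text says only that patients with the higher "score will be randomized in a 1:1 fashion to ticagrelor" or clopidogrel. It gives no stratum, block size or other method.

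In Figure 1, the row "Two CYP2C19 LOF alleles" carries +24 and one LOF allele +6. Age and BMI carry +4 each, and chronic kidney disease and diabetes +3 each.

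The statistical section specifies the primary comparison as "an analysis of covariance with a general linear model with baseline value of the corresponding platelet function test as a covariate". It names no other covariate. The baseline draw is described as "baseline (while on standard of care DAPT therapy): day after PCI". The P2Y₁₂ inhibitor used at PCI may be clopidogrel, ticagrelor or prasugrel, and sampling after the day's dose is allowed.

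**The concern.** The Background presents the score as a way to find patients with high platelet reactivity, that is, poor response to clopidogrel. On that premise LOF status should predict day-30 PRU, at least on clopidogrel. It is complete for all randomised patients and precedes allocation, yet the plan uses it only to form the cohort.

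With about 17 to 21 patients per arm, simple randomisation can leave the arms visibly uneven in carriers. If that happens, a reader will ask whether the PRU difference partly reflects the genotype split. Adding the factor after seeing an imbalance would be a data-driven choice; naming it beforehand avoids that. At stake are some precision and the ease of interpreting a small trial.

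**Working it through.** **Inputs from the documents.** SDs of 55 (ticagrelor) and 80 (clopidogrel) PRU; target difference 90 PRU; 90% power; two-sided alpha 0.05; 17 evaluable and up to 21 randomised per arm; the Figure 1 points.

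**Assumed, because the documents are silent.** Carrier share p of 0.3–0.7 in the ≥10 cohort; carriers D = 0–80 PRU higher on clopidogrel only, with a variant of 60 PRU higher in both arms. Simulations also assume a baseline correlation of 0.3.

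**1. The plan's own figure.** With (1.960 + 1.282)² = 10.51, SD 80 in both arms gives n = 2 × 80² × 10.51 / 90² = 16.6, so 17 per arm, as stated. The two stated SDs give (80² + 55²) × 10.51 / 90² = 12.2, so 13 per arm (14 by a t calculation). The stated 17 therefore already holds some reserve.

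**2. Does the cut-off fix genotype?** There are 16 combinations of the four clinical items.
- No LOF allele: 5 of 16 reach 10 (any three items, or all four).
- One allele: 13 of 16.
- Two alleles: all 16.

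These are counts of combinations, not patient frequencies, but they show that all three genotype groups can enter the randomised cohort.

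**3. Chance imbalance.** Taking carriers per arm as two independent Binomial(21, p) counts, the arms differ by 5 or more carriers in 12.8% of trials (p = 0.3 or 0.7) to 16.4% (p = 0.5). At 17 per arm it is about 9–12%.

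**4. Shift from a 5-carrier difference.** Measured against an even split of the same patients, a clopidogrel-only effect shifts the estimate by (5/21)/2 × D: 4.8 PRU at D = 40 and 9.5 PRU at D = 80. The standard error at 21 per arm is √((80² + 55²)/21) = 21.2 PRU, so the shift is about 0.2 to 0.45 standard errors.

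**5. Variance removed by stratifying and adding the term, before baseline adjustment.** Under simple allocation the carrier share in the clopidogrel arm varies with variance p(1−p)/n; with balanced arms this falls to p(1−p)/(2n). The proportional saving is D²p(1−p)/2 ÷ (80² + 55²).
- D = 0: none.
- D = 40: 1.8–2.1%.
- D = 60: 4.0–4.8%.
- D = 80: 7.1–8.5%.

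If the effect is D in both arms, the saving is 2D²p(1−p) ÷ 9,425. At D = 60 that is 1,512/9,425 = 16.0% (p = 0.3 or 0.7) to 1,800/9,425 = 19.1% (p = 0.5).

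**6. Simulation at 17 per arm with baseline adjustment.**
- Stratifying plus the term changed the variance by about zero for small effects, by −7% to −9% for 80 PRU on clopidogrel only, and by about −18% to −20% for 60 PRU in both arms.
- Power of the planned ANCOVA was 96–97% with the two stated SDs. It moved by about 1 point or less in the clopidogrel-only case and reached about 98–99% with 60 PRU in both arms.
- The covariate without stratification raised the variance by about 2–4% for clopidogrel-only effects up to 40 PRU.
- Type I error was about 5% with or without the term.

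**The case against.** The strongest reply is that nothing is broken. A randomised comparison adjusted for baseline is unbiased, and the planning SD of 80 is a total SD, so genotype variance and chance imbalance are already in the standard error. The 5–10 PRU shift in step 4 is part of that error and must not be counted on top of it. All of this stands.

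Four further points are partly right.

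- *Score points are not shares of PRU variance.* A reader might infer that genotype is the main driver of PRU in this cohort. The documents do not show that. The points predict high platelet reactivity, the clinical items together total 14 against 6 for one allele, and non-carriers enter only with three or four risk items, which may narrow the contrast. The assumed range therefore starts at zero.
- *Baseline PRU may already carry genotype.* It can in patients sampled on clopidogrel, which the Background calls the agent of choice here. It is a poor stand-in for clopidogrel response in those given ticagrelor or prasugrel at PCI, and the timing relative to the dose varies.
- *The plan is silent and does not refuse.* A reader might infer that stratification was considered and rejected, or that genotype will go unreported. Neither follows. No randomisation method is described, and genotype could appear among the categorical baseline characteristics.
- *Two levels pool one and two alleles.* This leaves the +6 versus +24 contrast unadjusted. That is a real limit, accepted because a third level risks near-empty strata at 17–21 per arm.

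**Conclusion.** The point holds as a modest, inexpensive improvement. LOF status is known for everyone before allocation, has the largest single weights in the score and is not fixed by the ≥10 cut-off, yet it is neither a stated stratum nor a term in the primary model.

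Under the assumed inputs, using it in both places reduces the variance of the primary difference by about 0–9% if genotype matters on clopidogrel only, and by about 16–20% for a 60 PRU effect in both arms. Neither prevalence nor effect size comes from the documents, so these are ranges and not forecasts.

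A reader might go further and infer that the primary estimate is biased or the conclusion at risk. The documents do not support that: randomisation protects the comparison, type I error is sound, and the change in power is small against a 90 PRU target.

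**What to change.** 1. In Study design, in both places where the 1:1 allocation is described, state that randomisation of the ≥10 cohort is stratified by LOF carrier status (no allele versus one or two).
2. In the statistical section, add the same two-level factor to the primary PRU ANCOVA beside baseline PRU. A main effect is enough.
3. Tabulate day-30 PRU by arm and LOF status, labelled descriptive.

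If randomisation is already complete without stratification, leave the primary model as it is, because the covariate alone may slightly widen the interval. Prespecify the genotype-adjusted model as a sensitivity analysis instead.

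The cost is a revised randomisation list, a few sentences and one model degree of freedom. No new data are needed, since the genotype is already required before allocation.

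### Two sites and about 42 randomised patients, but no site stratification is described and the primary ANCOVA has no site term: a modest, cheaply avoided loss of precision

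*Combined protocol and SAP*

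**What the plan says.** All references are to section 6 (Research Plan) of the combined protocol and SAP.

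- **Sites.** Study design names Jacksonville "and at St. Antonius Hospital in Nieuwegein, The Netherlands". The expected split of patients is not given.
- **Allocation.** In the high-score cohort, patients "will be randomized in a 1:1 fashion to ticagrelor" or clopidogrel. Sequence generation, blocking, concealment and strata are not described. The one stratification mentioned is that "patients will be stratified according to their ABCD-GENE score (using a cut-off of 10) into two cohorts". It forms the cohorts, so it balances nothing within the randomised comparison.
- **Numbers.** The sample size text plans up to 21 per randomised group, 42 in all.
- **Primary analysis.** The statistical section specifies an "analysis of covariance with a general linear model with baseline value of the corresponding platelet function test as a covariate". No other term is named.
- **Site code.** The same section says "Data from The Netherlands will arrive coded so that source of data can be easily known". No analytic use is given for that code.
- **Assays.** Laboratory assessments sets a two-hour limit for VerifyNow and LTA. It also assigns every assay except thrombin generation to the Jacksonville laboratory.

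**The concern.** The primary endpoint is a VerifyNow measurement, and blood drawn in Nieuwegein cannot be tested in Jacksonville within two hours. Local Dutch runs are therefore the likely intention, whatever the sentence that places the assay in Florida says. Two laboratories on two continents, serving two patient populations, could well differ in mean PRU.

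With about 21 patients per arm, simple 1:1 allocation can leave the sites unevenly spread between arms by chance. A site difference in PRU then becomes extra variation in the ticagrelor-clopidogrel contrast. A model without site cannot remove it, except for the part already carried by baseline PRU. At stake is some precision in a small trial, and a primary estimate that does not account for a known feature of the design.

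**Working it through.** **Inputs from the plan** (statistical section): SD 55 PRU (ticagrelor) and 80 PRU (clopidogrel); target difference 90 PRU; 90% power; two-sided alpha 0.05; 17 evaluable and up to 21 randomised per arm.

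**Assumptions** (not in the documents): 8 to 21 of the 42 patients at the smaller site; a site difference of 30 PRU, or 0 to 60 PRU in the simulation.

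**1. The plan's own figure.** Using the larger SD in both arms, n = 2 × (1.96 + 1.2816)² × 80² / 90² = 2 × 10.507 × 0.790 = 16.6, so 17 per arm. The stated figure is reproduced.

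**2. Chance imbalance in site.** With m patients at the smaller site and 21 v 21 allocated without regard to site, the between-arm difference in site share has SD = √[m(42 − m)/41] / 21.

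- m = 8: √(8 × 34/41) / 21 = 2.576/21 = 12.3 percentage points
- m = 12: √(12 × 30/41) / 21 = 14.1 points
- m = 16: √(16 × 26/41) / 21 = 15.2 points
- m = 21: √(21 × 21/41) / 21 = 15.6 points

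Over these four splits, a gap of 4 or more patients between arms has probability of about 22% to 34%. A gap of 6 or more has probability of about 4% to 11%.

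**3. Effect on the estimate.** For a 30 PRU site difference, the 95% range of the chance shift, before baseline adjustment, is:

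- m = 8: ±1.96 × 0.123 × 30 = ±7.2 PRU
- m = 21: ±1.96 × 0.156 × 30 = ±9.2 PRU

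These are 95% ranges, not maxima.

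**4. Against the sampling error.** The unadjusted standard error at 21 per arm is √[(55² + 80²)/21] = √448.8 = 21.2 PRU. If the stated SDs are within-site, the shift (SD 3.68 to 4.69 PRU) raises it to √(448.8 + 13.5) = 21.5 or √(448.8 + 22.0) = 21.7, which is 1.5% to 2.4%. If the SDs already include site variation, this noise is already counted.

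**5. Price of a site term.** At 17 per arm, residual degrees of freedom fall from 31 to 30. Noncentral-t power is 95.9% in both cases with the two stated SDs, and 88.8% v 88.7% with SD 80 in both arms.

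**6. Simulated power.** Settings: 17 per arm, SDs 55 and 80, effect 90 PRU, 6,000 runs per row. The simulated baseline carries no information, so it absorbs none of the site effect.

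| Site effect (PRU) | Smaller-site share | Unstratified, no site term | Unstratified, site term | Stratified, site term |
|---|---|---|---|---|
| 0 | 30% | 95.6% | 94.8% | 95.2% |
| 0 | 50% | 95.6% | 94.9% | 94.6% |
| 40 | 30% | 93.7% | 94.2% | 94.4% |
| 40 | 50% | 93.7% | 94.6% | 94.8% |
| 60 | 30% | 92.2% | 94.6% | 95.4% |
| 60 | 50% | 91.6% | 94.4% | 95.2% |

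The simulation error of each entry is about √(0.95 × 0.05/6000) = 0.3 points. In a stratified layout treatment and site are nearly orthogonal, so the true cost at zero site effect is close to step 5. The 0.4 to 1.0 point gaps in the first two rows are mostly simulation noise.

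**7. Simulated type I error.** Without a site term and without stratification it was 4.4% to 5.4% over site effects of 0 to 60 PRU. With stratified allocation and site left out of the model, it fell to 3.6% at 60 PRU, so the test becomes conservative.

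**The case against.** The strongest reply is that randomisation already deals with this. Imbalance in site is chance variation, the type I error holds, and no plausible site effect would overturn a 90 PRU difference. Omitting site is a legitimate choice in a small two-site pharmacodynamic study, and the source code allows a sensitivity analysis later. A constant offset in a local assay would also appear in baseline PRU and be partly adjusted. All of this stands, and it is why the point is minor. It does not make the omission preferable: the site term is almost free and protects power if sites differ. Baseline is also an imperfect substitute, because it is taken on whichever agent was used at PCI, and pre-dose sampling is only the ideal.

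Three stronger readings are tempting, and the documents do not support them.

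- *Allocation is unblocked, so arm sizes may drift apart.* The plan is silent on method; it does not say that blocks are absent. Equal groups are planned (20 and 20 under Study population, up to 21 each in the sample size text), which argues against a coin toss for each patient.
- *Sites differ in genotyping route or in the agent used at PCI.* Genotyping is done "using the Spartan assay or central lab", and the choice of P2Y12 "inhibitor during the PCI procedure may vary", but neither is tied to a hospital. Genotyping also acts before randomisation, on cohort entry, and baseline PRU takes up part of any difference due to the PCI agent.
- *Drug and site are confounded.* They are not. Both treatments are allocated at random, and severe imbalance is uncommon.

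**Conclusion.** The point holds as a low-severity improvement to design and analysis. No site stratification is described and the primary model has no site term, although site is recorded and the two-hour limit makes separate local VerifyNow runs likely. The consequence is noise: about ±7 to ±9 PRU (95% range, before baseline adjustment) against a 90 PRU target, if 8 to 21 patients come from the smaller site and the sites differ by 30 PRU. Neither figure is in the documents. With no site effect nothing is lost. At 40 to 60 PRU, the simulation suggests that stratifying and adjusting recovers roughly 1 to 4 points of power.

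A reader might infer a biased treatment effect or an inflated false-positive rate. Neither follows, since simulated type I error stayed near 5%. The conflict over where VerifyNow is run on Dutch samples is a matter of text and needs reconciling whatever is decided about the model.

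**What to change.** 1. **Study design.** State the method, for example: *Randomisation will be 1:1 in concealed permuted blocks of varying size, stratified by site (Jacksonville, Nieuwegein).* Varying block sizes matter because treatment is open-label.
2. **Statistical section.** Specify: *The primary ANCOVA will include treatment and site as fixed factors and baseline PRU as a covariate.* Make changes 1 and 2 together, because stratifying without the site term makes the test conservative.
3. **Laboratory assessments.** Reconcile the two-hour limit with the sentence placing VerifyNow and LTA at Jacksonville, and state where Dutch samples are run.

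The cost is a second randomisation list and one residual degree of freedom (31 to 30 at 17 per arm), with negligible loss of power if the sites do not differ. No patients, visits or data are added. If recruitment has begun, the site term can still be specified before the primary data are analysed; in the table above it recovers most of the gain on its own.
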